## 5. A Priori Statistical Methods

### 5.1. Study Design

\*Eligibility period determined between a minimum of 30 days and a maximum of 40 days. Investigators may have up to 5 additional days (beyond the 40 days) if needed to schedule patients' Visit 3 appointment.

aPatients randomized to the 120 mg dose will receive a loading dose of 240 mg at the first injection only (Visit 3).

Approximately 240 enrolled patients roll-over to I5Q-JE-CGAP study (Open Label Extension) at visit 12

Abbreviations: SP = study period.

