**Table CGAN. 5.2 ePRO Diary Questions, Responses, and Assignment to Headache Type**

QUESTION	RESPONSES	HEADACHE ASSIGNMENT
Q1. Yesterday, did you have a headache that lasted for thirty minutes or more?	Yes	Migraine if at least two migraine Criteria A's and at least one migraine Criteria B.
	No a	
Q2. Enter the total number of hours you had a headache yesterday.	Range 1 to 24	If $\geq 1$ , the headache will be counted as a headache day.
Q3. Yesterday, what was the worst headache pain?	Mild	
	Moderate	Migraine Criteria A
	Severe	Migraine Criteria A
Q4. Yesterday, was the headache throbbing or pounding?	Yes	Migraine Criteria A
	No	
Q5. Yesterday, was the headache just on the right or left side of your head?	Yes	Migraine Criteria A
	No	
Q6. Yesterday, was the headache made worse by your usual daily activity?	Yes	Migraine Criteria A
	No	
Q7. Yesterday, did the headache come with sensitivity to light and sound?	Yes	Migraine Criteria B
	No	
Q8. Yesterday, did you feel sick to the stomach or throw-up with the headache?	Yes	Migraine Criteria B
	No	
Q9. Yesterday, did you have your menstrual period (if female)?	Yes	
	No	
Q10. Yesterday, did you take any medicine for your headache?	Yes	Medication will only count as headache medication on a day a headache occurred.
	No	
Q11. Yesterday, did you take any medication for pain other than headache?	Yes	
	No	
Q12. Yesterday, did you experience aura?	Yes	
	No	
Q13. Yesterday, did you experience any warning symptoms other than aura (prodrome symptoms) that a migraine was coming?	Yes	
	No	

a If "No" is answered for Q1, then the patients will skip Q2 - Q6, only answer questions Q7 - Q13.

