- **Number of migraine headache days with menstrual period** is calculated as the total number of migraine headache days with an answer of “yes” to Question 9 in a 30-day period. (Note: The analysis population is based on female who have at least one “Question 9 =Yes” through the entire study in CGAN.
- **Number of days with abortive medication use on non-headache days** is calculated as the number of calendar days in a 30-day period on which an abortive medication is used and “Question 1 = No”.

The following analysis is based on weekly data:

- **Number of weekly migraine headache days in Month 1** is calculated as the number of migraine headache days in a 7-day period on which a migraine headache occurs. At Month 1, the first 7 calendar days will be counted as week 1, the second 7 calendar days will be counted as week 2, the third 7 calendar days will be counted as week 3, the rest of the calendar days (up to Visit 5 – 1 day) will be counted as week 4. If diary is missing on a certain day, then it is counted as non MHD day. If patients discontinues early, then the rest of the days are considered non MHD day.

**Example:** Suppose duration of Visit 3 (2018/Jan/1) and Visit 5 (2018/Jan/31) is 30 days. Then duration of week 4 is 9 days with Jan/22, Jan/23, ..., Jan/30. Note that Jan/31 is counted for Month 2.

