**Table CGAN. 5.5 Primary, Secondary and Exploratory Efficacy Variables and Analysis Methods**

Efficacy Variables	Analysis in SP III	Analysis in SP III/IV	Analysis in SP IV only
Number of MHD	MMRM/ANCOVA	MMRM	NA
Number of MHD with Criteria C	MMRM	NA	NA
Number of migraine headache hours	MMRM	NA	NA
Number of migraine attacks	MMRM	NA	NA
Number of days with acute medication use	MMRM	NA	NA
Number of MHD with acute medication use	MMRM	MMRM	NA
Proportion of MHD with acute medication use	MMRM	NA	NA
Number of headache days	MMRM	NA	NA
Number of moderate-severe headache days	MMRM	NA	NA
Number of headache hours	MMRM	NA	NA
Number of ICHD MHD	MMRM	NA	NA
Mean severity of migraine headache	MMRM	NA	NA
Number of MHD with nausea and/or vomiting	MMRM	NA	NA
Number of MHD with photophobia and	MMRM	NA	NA

phonophobia			
Number of MHD with aura	MMRM	NA	NA
Number of MHD prodrome symptoms other than aura	MMRM	NA	NA
Number of non-MHD with aura	MMRM	NA	NA
Proportion of Aura within migraine attack	MMRM	NA	NA
Number of classes of acute medication use	MMRM	NA	NA
Number of classes of acute medications used on MHD	MMRM	NA	NA
Average number of classes of acute medication use	MMRM	NA	NA
Average number of classes of acute medication use on MHD	MMRM	NA	NA
Number of MHD with menstrual period	MMRM	NA	NA
Number of days with triptans use	MMRM	NA	NA
Number of MHD with triptans use	MMRM	NA	NA
Number of days with NSAIDS/Aspirin use	MMRM	NA	NA
Number of MHD with NSAIDS/Aspirin use	MMRM	NA	NA
Number of days with Acetaminophen/paracetamol use	MMRM	NA	NA
Number of MHD with Acetaminophen/paracetamol use	MMRM	NA	NA
Number of days with Ergots use	MMRM	NA	NA
Number of MHD with Ergots use	MMRM	NA	NA
Number of days with Anti-nausea use	MMRM	NA	NA
Number of MHD with Anti-nausea use	MMRM	NA	NA
Number of days with Multi-Class acute medication use	MMRM	NA	NA
Number of MHD with Multi-Class acute medication use	MMRM	NA	NA
Number of days with acute medication use on non-headache days	MMRM	NA	NA
PGI-S	MMRM	MMRM	NA

PGI-I (adjusting for PGI-S)	MMRM	NA	NA
MSQ Total	MMRM	MMRM	NA
MSQ Role Function-Restrictive domain	MMRM	MMRM	NA
MSQ Role Function-Preventive domain	MMRM	MMRM	NA
MSQ Emotional Function domain	MMRM	MMRM	NA
MIDAS Total (sum of item 1, 2, 3, 4, and 5)	MMRM	MMRM	NA
MIDAS individual items (item 1, 2, 3, 4, 5, A, and B)	MMRM	NA	NA
HCRU Summary	Descriptive	NA	Descriptive
HCRU Migraine related events/100-patients-year	Descriptive	NA	Descriptive
HCRU Employment status	Descriptive	NA	Descriptive

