**Table CGAN. 5.9 Unblinded members through CGAN Study**

Role	Reason	Data source for unblinding
Product Delivery personnel	To provide and manage Clinical trial materials	e-CTS
Clinical Laboratory Operations	To manage and track sample shipping	CLRM
Unblind Case Manager	To report SAE with unblinded information to EU authority	e-CTS
Data Movement	To transfer unblinded data at the timing of interim DBL (and final DBL)	source data of CLUWE

Abbreviations: CLRM = Clinical Laboratory Results Modernization; DBL = database lock; e-CTS = Enhanced Clinical Trials System; EU = European Union; GPS = Global Patient Safety; IWRS = interactive web-response system; PK/PD = pharmacokinetics/ pharmacodynamics; SAE = Serious Adverse Event.

The interim analysis will be conducted by selected unblinded study team members who do not have direct interaction with sites (Table CGAN. 5.10). These members will become unblinded after the interim database lock. All study personnel with direct interaction with sites are kept blinded to the interim analysis results.

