## 5.8. Reports to be Generated at Interim and Final Database Lock

### 5.8.1. Report to be Generated at Interim Analysis

At the time of interim analysis, all randomized patients will have had the chance to complete 6 months of treatment. The following analyses will be conducted for pre-specified population (e.g. ITT, safety population) in the SAP who have had a chance to complete 6 months of treatment:

- Patient disposition as specified in Section 5.5.2, but for Study Period III only.
- Protocol deviations as specified in Section 5.5.3, but for Study Period III only.
- Patient Characteristics as specified in Section 5.5.4.
- Exposure to Investigational Product as specified in Section 5.5.5.

- Treatment Compliance as specified in Section 5.5.6.
- ePRO Diary Compliance as specified in Section 5.5.7, but for Study Period III only.
- Previous Migraine Prevention Therapy and Previous Migraine Acute Treatment as specified in Section 5.5.8.
- Concomitant Therapy, Migraine Prevention Therapy and Migraine Acute Treatment as specified in Section 5.5.9, but for Study Period III only.
- All efficacy, quality-of-life and safety analyses as specified in Section 5.5.10, Section 5.5.11 and Section 5.5.12, but for Study Period III only except immunogenicity related analysis. Immunogenicity related analysis will not be conducted at the interim DBL because some data during SP III will not be included in the interim DBL due to time lag.
- Subgroup analyses as specified in Section 5.5.13.
- Bridging Criteria as specified in Section 5.10.

Some TFLs at interim analysis may contain both SP III and SP IV data (e.g. HCRU summary). Those TFLs will be updated at the final DBL.

Analysis for “SP III and SP IV combined” and “SP IV only” (e.g. time from the end of SP III to start of migraine prevention treatment in SP IV), and ADA related analysis will be based on the final DBL.

The TFLs for SP III only (i.e. no use of SP IV data) based on the interim DBL will be used in the final study Clinical Study Report (CSR) except for some TFLs needed to be updated. Hence analysis conducted at the interim DBL which do not include SP IV data will not be refreshed at the final DBL unless otherwise specified. Those TFLs will be specified and explained in CSR, if they exist.

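### The population for migraine days with menstrual period draws on diaries up to the end of Study Period IV, although the analysis covers only Study Period III and is run at the interim lock

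*SAP*

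**What the plan says.** SAP 5.4.1 lists this measure among the additional efficacy measures that are neither secondary nor exploratory. The count "is calculated as the total number of migraine headache days with an answer of “yes” to Question 9 in a 30-day period". A note sets the population: "The analysis population is based on female who have at least one" Yes to Question 9, counted "through the entire study in CGAN". The same section has patients completing the diary daily from Visit 2 to Visit 14, so the window runs from baseline to Month 10.

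In Table CGAN. 5.5 the row "Number of MHD with menstrual period" has an MMRM for Study Period III and NA for both Study Period III/IV and Study Period IV. SAP 5.5.10.3 makes the outcome the change from baseline.

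SAP 5.6 places the interim analysis at the point where every randomised patient has had the chance to finish Study Period III. SAP 5.8.1 runs the Study Period III efficacy analyses at that lock. Analyses that do not include Study Period IV data "will not be refreshed at the final DBL unless otherwise specified". The same section says that outputs containing data from both periods are updated at the final lock. Of the statistician, programmers and others listed for the interim, SAP 5.7 says "These members will become unblinded after the interim database lock".

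SAP 5.1 adds: "Approximately 240 enrolled patients roll-over to I5Q-JE-CGAP study". Protocol 7.8.1 states that these patients skip Study Period IV.

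**The concern.** The selection window is longer than the analysis window. Three things follow.

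- **Follow-up.** Whether a woman is in the analysis can depend on what she recorded after randomisation and on how long she kept a diary. Roll-over patients have no Study Period IV diary at all.
- **The lock.** The set described cannot be complete at the lock where the table is produced.
- **Forced zeros.** A woman brought in only by a later Yes has no menstrual day in the baseline data. Her baseline count must be 0, and her change can only be 0 or positive. Such women pull the mean change upwards in whichever arm they belong to.

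At stake are a table that can be reproduced from its definition and an estimated reduction that is not diluted by women who cannot show one. The primary result is not involved.

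**Working it through.** **Who can supply Study Period IV diaries.** Inputs from SAP 5.1 and 5.2: 451 randomised, 15% discontinuation, about 240 rolling over.

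- Completers: 451 × 0.85 = 383.35; the plan states 383, so its figure is reproduced.
- Roll-over patients must complete Study Period III, so about 240/383 = 63% of completers stop CGAN diaries at Visit 12. The other 383 − 240 = 143 (37%) can continue.
- At most 451 − 240 = 211 patients (47%) can enter Study Period IV.
- Diary months: baseline + 6 = 7 for a roll-over patient; baseline + 6 + 4 = 11 for a completer who stays.

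**Does length of follow-up change selection?** The documents give no menstrual data. Assume a chance q of any menstrual day in a month, constant and independent across months. The chance of selection over m diary months is 1 − (1 − q)^m.

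| q | 2 months | 7 months | 11 months |
|---|---|---|---|
| 0.95 | 99.7% | 100% | 100% |
| 0.5 | 75% | 99% | 100% |
| 0.2 | 36% | 79% | 91% |

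The chance of entering only through Study Period IV, (1 − q)^7 × [1 − (1 − q)^4], is practically 0 at q = 0.95, 0.7% at 0.5 and 12% at 0.2. Follow-up matters only for women who menstruate rarely.

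**How many zeros does the rule force?** Among women selected over baseline plus six months, the share with no menstrual day in the baseline month is (1 − q)[1 − (1 − q)^6] / [1 − (1 − q)^7]. This is 5% at q = 0.95, 50% at 0.5 and 75% at 0.2.

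**Whom would a baseline rule leave out?** Assume 5 bleeding days per cycle of length C and a window of W days. The chance of no bleeding day in the window is max(0, (C − 5) − W + 1)/C.

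- W = 30: 0 for C up to 32; 1/35 = 3%; 6/40 = 15%; 11/45 = 24%; 26/60 = 43%.
- W = 40: 1/45 = 2%; 16/60 = 27%.

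**Which zeros would remain under a baseline rule?** The endpoint needs migraine and menstruation on the same day. With 5 bleeding days in 30, placed independently of m migraine days, the chance of no overlap is C(25, m)/C(30, m), where C(n, k) is the binomial coefficient. That gives 46% at m = 4, 18% at m = 8 and 3% at m = 14 (the eligible range is 4 to 14). Positive association would lower these figures.

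**Which refresh rule applies?** The outcome data are Study Period III only, which points to no refresh. The population uses Study Period IV diaries, which points to an update. SAP 5.8.1 expressly defers immunogenicity but does not mention this output, so either reading is open.

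**The case against.** A reader might infer more than the documents support, and most of the counter-case is sound.

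- *The population is chosen from post-randomisation diaries.* Only partly. Baseline diaries count too, and later diaries can only add women.
- *Early stoppers are shut out.* Patients who discontinue in Study Period III are expected to enter Study Period IV (Protocol 5.1 and 8), where diaries continue. Someone who stops at Month 1 and completes follow-up has 1 + 1 + 4 = 6 diary months, against 7 for a roll-over patient.
- *The table is certain to be frozen on a partial set.* The no-refresh rule is limited to analyses without Study Period IV data, so a route to an update exists. The text does not say which rule applies here.
- *Updating after unblinding invites bias.* Membership is a mechanical yes/no on patient-entered data, and sites and patients stay blinded in Study Period IV. No mechanism is shown.
- *The arm comparison is biased.* That would need menstruation or follow-up to differ by arm, and nothing in the documents quantifies this. The MMRM also adjusts for baseline and baseline-by-month, and zeros in every arm do not by themselves bias a randomised contrast.

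SAP 5.5.10.3 also allows change-from-baseline results to be left out of the CSR where baseline values are very low. Using all diaries to separate menstruating from non-menstruating women aged 18 to 65 is a reasonable aim.

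What still stands is that the rule as written cannot be applied in full at the lock where the table is produced, and that it admits women whose baseline is forced to 0.

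**Conclusion.** The point holds as a defect of definition with small impact. Membership depends partly on later diaries and follow-up, it cannot be complete at the interim lock, and the SAP does not say which set the reported table will use. The number of women affected cannot be computed from the documents. Under the stated assumptions, follow-up barely changes selection for regular cyclers (99.7% or more with 2, 7 or 11 diary months), and about 5% of those selected would have a forced zero. The shares become large only when menstruation is infrequent. The measure carries no multiplicity control and lies outside the secondary and exploratory lists. No between-arm bias is demonstrated, and the primary analysis is untouched. This is an inexpensive improvement, not a threat to the trial's conclusions.

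**What to change.** Replace the note in SAP 5.4.1 by: *the analysis population is female ITT patients with at least one Question 9 = Yes from Visit 2 to the eligible day (the diary days used for the efficacy baseline).* The end point should be the eligible day, not Visit 3. SAP 5.4.1 discards diaries between the two, so a woman whose only Yes fell there would again have a forced zero. Table CGAN. 5.8 already uses this kind of baseline-diary rule for the aura subgroup.

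Membership is then settled before dosing, is the same at both locks, and produces no zeros forced by selection. Women who menstruate at baseline but have no migraine on those days will still have a baseline of 0, so not every baseline can fall.

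The cost is one sentence and one program filter. A few women with long or irregular cycles drop out, and selecting on a baseline Yes may bring some regression to the mean, equally in all arms. If a wider set is wanted, limit it to baseline plus Study Period III and report it as a sensitivity analysis.

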## **5.4.2. Other Efficacy Measures**

### **5.4.2.1. Patient Global Impression**

#### **5.4.2.1.1. PGI-S (Patient Global Impression of Severity)**

The Patient Global Impression of Severity (PGI-S) will be collected at baseline and monthly post-baseline visits (Month 1, Month 2,..., Month 6) in SP III and visit 14 (Month 10) in SP IV. In this single-item scale, patients rate the severity of their migraine condition on a scale ranging from “not at all ill”(coded as 1) to “extremely ill” (coded as 7).

PGI-S responder at each visit is defined as having a severity decrease from baseline of at least 2 points on the 7-point scale at the specific visit. The model estimates mean percentages of patients meeting this definition of response over the final 3 months of double-blind treatment (average of Months 4 to 6).

**5.4.2.1.2. PGI-I (Patient Global Impression of Improvement)**

CCI

CCI

[Redacted]

[Redacted]

[Redacted]

[Redacted]

[Redacted]

[Redacted]

[Redacted]

CCI

CCI

CCI

CCI

### **5.4.3. Quality of Life Questionnaires**

#### **5.4.3.1. Migraine Specific Quality of Life (MSQ) v2.1**

Migraine Specific Quality of Life (MSQ) v2.1 consists of 14 questions. The questions measure the impact of migraine on health-related quality of life across three domains: 1) Role Function-Restrictive (7 questions), examines the degree to which performance of daily activities is limited by migraine; 2) Role Function-Preventive (4 questions), examines the degree to which performance of daily activities is prevented by migraine; 3) Emotional Function (3 questions), examines feelings of frustration and helplessness due to migraine.

Precoded item values and final item values for each MSQ item response are shown in [Table CGAN. 5.3](#). All item values range from 1 to 6. Final item value will be used as for analysis with higher score reflecting better quality of life.

**Table CGAN. 5.3 Item Values for Migraine Specific Quality of Life (MSQ) Item**

Response Categories	Precoded Item Value	Final Item Value
None of the time	1	6
A little bit of the time	2	5
Some of the time	3	4
A good bit of the time	4	3
Most of the time	5	2
All of the time	6	1

Questions 1 to 7 of the questionnaire will be grouped together as Role Function-Restrictive domain, questions 8 to 11 as Role Function-Preventive domain, and questions 12 to 14 as the Emotional Function domain.

The score of each domain will be calculated as the sum of the final item values of each question in that domain, using imputed scores where applicable.

When the number of missing items is fewer than or equal to 3 for the Role Function-Restrictive domain, the value of missing item(s) can be estimated using the average of the other completed items within the same domain. Similarly, when the number of missing items is fewer than or equal to 2 for the Role Function-Preventive, and fewer than or equal to 1 for the Emotional Function dimension, the value of missing item(s) can be estimated using the average of the other completed items within the same domain.

If the number of missing responses was more than half the questions in a domain, meaning that imputation of missing scores will not be done, then the score for that domain will not be calculated, hence set as missing.

The total score of all three domains will be calculated as the sum of raw scores of three domains. If any of the three domain scores is missing, then total score will be missing.

In addition, the raw scores of each domain and the total score will be transformed to a 0 to 100 scale using the following formulae:

- Role Function-Restrictive (range of 7 to 42):

$$\frac{(\text{raw score} - 7) \times 100}{35}$$

- Role Function-Preventive (range of 4 to 24):

$$\frac{(\text{raw score} - 4) \times 100}{20}$$

- Emotional Function(range of 3 to 18):

$$\frac{(\text{raw score} - 3) \times 100}{15}$$

- Total Score (range of 14 to 84):

$$\frac{(\text{raw total score} - 14) \times 100}{70}$$

The MSQ Role Function-Restrictive domain responder is defined as patients with the change from baseline sub score  $\geq 25$  (average of Month 4, 5, and 6). If one or two months are missing for the domain, then take the average from the existing months' domain. If all months (Month 4, 5, and 6) are missing then the response value is set to missing.

#### 5.4.3.2. MIDAS (Migraine Disability Assessment) Questionnaire

The Migraine Disability Assessment questionnaire (MIDAS) consists of 5 questions (Q1-Q5) and two additional questions (A and B). The questionnaire measures the impact that migraine headaches have on migraineurs' life, including days of work or school missed, days with productivity at work or school reduced to half or more, days with household work missed, days with productivity in household work reduced to half or more, and days missed family / social / leisure activities. Each question is answered as a numeric number of days during the past 3 months of assessment, ranging from 0 to 90. The answers to all 5 questions will be added up to a total MIDAS score. No imputation is needed when calculating the total score as patients are not allowed to send partial data.

The MIDAS responders are defined as patients with  $\geq 50\%$  improvement in the total MIDAS score.

The total MIDAS score, the raw score of each question, and the indicator of MIDAS responders will be used as analysis values.

#### 5.4.3.3. HCRU (HealthCare Resource Utilization and Employment Status) Questionnaire and employment status

The Healthcare Resource Utilization (HCRU) will be solicited by study personnel while documenting patient responses. The HCRU consists of 3 questions;

1. Hospital emergency room visits since your last study visit (YES/NO)
  - a. If yes, how many times did you go to a hospital emergency room?
  - b. How many of these times going to a hospital emergency room were related to your migraine headaches?
2. Overnight stays as a patient in a hospital since your last study visit (YES/NO)
  - a. If yes, how many different times were you as a patient in a hospital overnight?

- How many days total were you in the hospital for overnight stay?
  - b. How many of these times, as a patient in a hospital overnight, were related to your migraine headaches?
  - c. How many days total, as a patient in a hospital overnight, were related to your migraine headaches?
3. Any other visits with a healthcare professional that occurred since your last study visit (YES/NO)
- a. If yes, how many different times did you visit a healthcare professional?
  - b. How many of these times, visiting a healthcare professional, were related to your migraine headaches?

Regarding question 3, patients are specifically asked about the number of healthcare events that are related to migraine headaches, outside of visits associated with their participation in the clinical trial.

The baseline visit will include the same questions, however, with the frame of reference being over the last 6 months.

A question on employment status is also solicited, given the correlation and potential confounding with health outcomes measures. More specifically, one of the following statuses with additional information will be recorded.

- Working for pay
  - average number of hours worked (hours/week)
  - how long has the patient had this job? (number of weeks)
- Student
- Keeping house (full-time)
- Volunteer work
  - average number of hours volunteered (hours/week)
- Unemployed, *not* due to study disease disability
- Unemployed, due to study disease disability
- Retired
- Self-employed

There will be no imputation for missing values.

